## **8. STATISTICAL ANALYSIS**

### **8.1 General Data Handling Rules and Definitions**

If any randomized subject is found to not have valid documented informed consent, that subject's data will be excluded from the report, except as necessary to document the error.

Except where specified all continuous variables will be summarized with descriptive statistics (the number of non-missing values, mean, standard deviation, median, minimum and maximum) and all categorical variables will be summarized with frequency counts and percentages, by treatment group.

Missing data will be maintained as missing unless specified otherwise (see Section 7.4.1 (number of migraine/headache days and associated calculations)). For variables where missing data is imputed, the analysis dataset will include an indication that it is imputed.

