### 5.1 Intent-to-Treat (ITT) Population

The Intention to treat (ITT) population includes all randomized subjects with at least one verified treatment post-training during the 12 week randomized period. The ITT population will be analyzed using the subject's randomized treatment regardless of which treatment the subject actually received.

The ITT is considered the primary analysis dataset, and will be used for all primary and secondary efficacy analyses.

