## 7.4 Efficacy

### 7.4.1 Primary Endpoint

The primary endpoint is the change from run-in to the last four weeks (Month 3) of the randomized period in the number of migraine days.

The diary data will collect for each day an indicator (1=Yes, 0=No, or missing) of whether the subject experienced a migraine. One 24 hour period per migraine will be designated as a migraine day.

The visit level value for a given subject is then the sum of the daily diary day indicators of whether the subject experienced a migraine which gives the number of days with a migraine. Calculations are as follows:

$$\text{Run-in Value} = \sum_{i=-z-28}^{-z} \text{Day } i, \text{ where Day } i = 1 \text{ (had a migraine)}$$

where  $z$  represents the subject's last day with diary data during the run-in period.

In the event that a subject does not 28 diary days in the run-in period the following rules will be used to calculate the run-in value:

1. If the number of diary days in the run-in period is less than 21, the run-in value will not be calculated, and will be considered missing.
2. If number of diary days in the run-in period is greater than or equal to 21, but less than 28, the run-in value would be calculated as:

$$\text{Run-in Value} = \sum_{i=-z-x}^{-z} \text{Day } i, \text{ where Day } i = 1 \text{ (had a migraine)}$$

where  $z$  represents the subject's last day with diary data during the run-in period, and  $x$  is the number of days with diary data during the run-in period.

To ensure consistency of the run-in value for all subjects, the value will be adjusted to reflect an estimated number of days with migraine per 28 day interval. For example, if a subject records data for  $x$  days out of 28 days and have  $y$  days with migraine, then the adjusted number of days with migraine in 28 days is  $(28/x)*y$ , with a maximum value of 28.

$$\text{Month 3 Value} = \sum_{i=57}^{84} \text{Day } i, \text{ where Day } i = 1 \text{ (had a migraine)}$$

In the event that a subject does not have at least 84 study days in the DB period the following rules will be used to calculate the Month 3 value:

3. If the number of study days in the DB period is less than 70, the month 3 value will not be calculated, but rather imputed to the run-in value (and thus resulting in a  $\text{Change}_{\text{Run-in}}=0$ , implying no change between periods).

Month 3 Value =Run-in Value

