4. If number of study days in the DB period is greater than or equal to 70, but less than 84, the month 3 value would be calculated as:

$$\text{Month 3 Value} = \sum_{i=1}^z \text{Day } i, \text{ where Day } i = 1 \text{ (had a migraine)}$$

where  $z$  represents the subject's last day of participation with diary data present.

To ensure consistency of this value for all subjects, the value will be adjusted to reflect an estimated number of days with migraine per 28 day interval. For example, if a subject records data for  $x$  days out of 28 days and have  $y$  days with migraine, then the adjusted number of days with migraine in 28 days is  $(28/x)*y$ , with a maximum value of 28.

Then the change from Run-in is calculated using the adjusted values as:

$$\text{Change}_{\text{Run-in}} = \text{Month 3 value} - \text{Run-In value}$$

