#### *HIT-6*

The total score on the HIT-6 is captured on the eCRF, but will be recalculated for analysis as the sum of the response to the questions. Should any question be blank or unanswered, no total score will be calculated. The HIT-6 eCRF will be completed at V2 (the end of the run-in period), V4, V5, V6 (the end of the randomized period), V8, V9, V10 (12 weeks following the start of the OL period), and at V12 (24 weeks following the start of the OL period). The change in the HIT-6 total score from the run-in period to each assessment will be calculated. Change in HIT-6 total score may also be calculated from the end of the DB period to each assessment in the OL period.

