### Shift in MIDAS Categories

In addition to the analyses described above, a shift analysis of the MIDAS level of disability categories from baseline to each later assessment will be presented for each treatment group. The proportion of subjects who shift from moderate or severe disability (Grade III or IV) during the run-in period to little or no disability (Grade I) and the proportion of subjects who shift from moderate or severe disability (Grade III and IV) to mild, little or no disability (Grade II and I) at each later assessment will be evaluated using a chi-square test.

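### MIDAS, HIT-6 and EQ-5D-5L at V6 are compared only among subjects with a score, while early dropouts stay in the diary endpoints as no change; unequal dropout can therefore bias the questionnaire results, in either direction

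*SAP*

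**What the plan says.** **Population.** SAP 5.1: "The ITT is considered the primary analysis dataset, and will be used for all primary and secondary efficacy analyses". That population "includes all randomized subjects with at least one verified treatment post-training during the 12 week randomized period", so a subject need not reach V6 to belong to it.

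**Diary endpoints.** SAP 7.4.1: "If the number of study days in the DB period is less than 70, the month 3 value will not be calculated, but rather imputed" as the run-in value, which makes the change zero. For a longer partial stay the rule differs: the diary data present are used and scaled to 28 days. That rule opens with the words "If number of study days in the DB period is greater than or equal to 70, but less than 84, the month 3 value would". A run-in with fewer than 21 diary days leaves the run-in value missing. Section 7.4.2 applies the same method to headache days and acute-medication days.

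**Questionnaires.** SAP 8.1: "Missing data will be maintained as missing unless specified otherwise (see Section 7.4.1 (number of migraine/headache days and associated calculations". Section 7.4.2 gives item-level rules only: a blank MIDAS or HIT-6 item means no total, and a missing EQ-5D-5L dimension means no index. It has no rule for a missing visit. MIDAS has one post-baseline score in the randomized period, at V6. HIT-6 has three: "The HIT-6 eCRF will be completed at V2 (the end of the run-in period), V4, V5, V6 (the end of the randomized period"). EQ-5D-5L follows the same schedule as HIT-6.

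**Analysis.** Section 8.4.2 compares the questionnaire scores between groups visit by visit, with confidence intervals. The MIDAS shift out of Grade III or IV "at each later assessment will be evaluated using a chi-square test", with no denominator stated. Section 8.4.1 restricts the multiple imputation and pattern-mixture analyses to data points imputed under 7.4.1.

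**The concern.** One withdrawn subject is handled in two ways under the same ITT label. A subject who leaves before Day 70 is a failure on the 50% responder endpoint but, read through section 8.1, absent from the MIDAS shift test, although both are responder-type outcomes.

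Two other parts of the SAP show the contrast. Section 5.2 lists not reaching visit 6 as a major deviation that removes a subject from the per-protocol population; the V6 MIDAS comparison in the ITT population applies the same exclusion in effect. Section 8.4.3.5 makes the analysis of non-imputed data an additional analysis for the diary endpoints; for the questionnaires, observed data are the only analysis.

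At stake is whether the disability and quality-of-life comparisons keep the protection of randomization. If the arms lose different numbers or kinds of subject, the V6 difference mixes treatment effect with selection. It could then disagree with the migraine-day result only because withdrawal was scored differently. An unstated shift denominator also leaves that choice open until results are known.

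**Working it through.** **1. The plan's own figures (SAP 3.5).** With a 1-day difference, SD 2.5, 5% two-sided alpha and 90% power, the two-sample t calculation gives 132.31, rounded up to 133 per group, which matches. Dropout inflation: 133/0.85 = 156.5, so 157; the plan states 160, within 3%.

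**2. Subjects affected.** 160 × 0.15 = 24 per arm could lack a V6 score, leaving 160 − 24 = 136. The diary analysis can keep all 160, given a valid run-in value.

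**3. How an early dropout scores.** Under 70 days, Month 3 equals run-in, so the change is 0 and the percentage reduction is −100 × 0/run-in = 0%. That is below 50%, a non-responder. On MIDAS the same subject has no V6 score and, under 8.1, no shift status.

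**4. Effect on the shift proportion.** Let p be the true proportion shifting among all randomized Grade III/IV subjects, d the dropout in an arm, and r the proportion of dropouts who would have shifted. Among those observed:

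p_obs = (p − d·r)/(1 − d)

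The SAP gives none of p, r or dropout by arm. Assume p = 30% in both arms (no true difference). Each dropout pair below averages the plan's 15%.

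| Dropout active / sham | r | Active | Sham | Difference |
|---|---|---|---|---|
| 15% / 15% | 0% | 35.3% | 35.3% | 0 |
| 20% / 10% | 0% | 0.30/0.80 = 37.5% | 0.30/0.90 = 33.3% | +4.2 |
| 10% / 20% | 0% | 33.3% | 37.5% | −4.2 |
| 25% / 5% | 0% | 0.30/0.75 = 40.0% | 0.30/0.95 = 31.6% | +8.4 |
| 20% / 10% | 30% | 30.0% | 30.0% | 0 |
| 20% / 10% | 60% | (0.30 − 0.12)/0.80 = 22.5% | (0.30 − 0.06)/0.90 = 26.7% | −4.2 |

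In the r = 0% rows, counting dropouts as not shifted over all randomized returns 30% versus 30%.

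**5. Effect on the test.** Take 160 Grade III/IV subjects per arm, an upper bound because not every subject need start there. Using the pooled two-proportion z test (equivalent to the uncorrected chi-square), 20%/10% with r = 0% gives a 10.7% chance of a false result for active instead of 2.5%; 25%/5% gives 30.3%.

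**6. Effect on a mean score.** Suppose the true mean change is −4 points in both arms (a fall being improvement) and dropouts do not change. With 20%/10% dropout the observed-case difference is −4/0.80 + 4/0.90 = −5.00 + 4.44 = −0.56 points in favour of active. Swapping the arms reverses the sign. The −4 is an assumption.

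**The case against.** The strongest defence is that nothing here contradicts the ITT definition. Section 5.1 fixes who belongs and that they are analysed as randomized; it does not promise imputation, and 8.1 openly declares that missing values stay missing. That stands: the issue is a weak analysis choice and an unstated denominator, not a broken definition.

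It is also true that no success rule is attached to these endpoints, that 8.1 reports non-missing counts and 8.2 reports withdrawals with reasons by arm, so unequal loss would be visible, and that the primary and 50% responder results are unaffected. The protocol may also provide for questionnaires at early termination, which would reduce the number missing. These points limit the weight of the concern. They do not supply a missing-visit rule or a sensitivity analysis.

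A reader might infer three stronger things that the SAP does not support:

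- *That the plan favours the arm losing more subjects.* This needs both unequal dropout and dropouts who do worse than stayers. The SAP gives a single overall 15% and says nothing on dropout outcomes; the table shows zero and reversed bias as well.
- *That withdrawn subjects disappear from all three questionnaires.* HIT-6 and EQ-5D-5L are also compared at V4 and V5, so a subject who leaves after V4 still contributes there. Only V6, and hence MIDAS in the randomized period, is confined to those who reach it.
- *That every withdrawal counts as no change on the diary.* This holds below 70 days only; at 70 to 83 days observed diary data are used, and a short run-in leaves the value missing.

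**Conclusion.** The concern holds in a conditional form. The V6 MIDAS, HIT-6 and EQ-5D-5L comparisons are observed-case by the general rule in 8.1. The MIDAS shift test is so by inference from that rule, because its denominator is not stated. The diary endpoints keep early dropouts as failures, and no planned sensitivity analysis covers the questionnaires.

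About 24 of 160 subjects per arm could be affected at the planned dropout. The possible distortion is about 4 points in the shift proportion at 20% versus 10% dropout if no dropout would have shifted, in the direction of the arm that loses more. It is zero if dropouts resemble stayers, or if dropout and dropout outcomes are equal in the two arms, and it reverses if dropouts improve more. These sizes rest on an assumed 30% shift rate and assumed dropout splits. The affected endpoints are secondary, so this should be corrected but does not threaten the primary conclusion.

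**What to change.** Amend SAP 8.4.2 before unblinding:

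1. **HIT-6 and EQ-5D-5L (index and VAS), randomized period.** Estimate the V6 difference from a repeated-measures model of change at V4, V5 and V6, with treatment, visit, treatment-by-visit, center and the V2 score. Keep the observed-case summaries as supportive.
2. **MIDAS shift at V6.** State the denominator as ITT subjects at Grade III or IV at V2, and count those who withdrew before V6 as not shifted. Report an observed-case analysis alongside. Limiting the rule to withdrawals avoids failing a completer who left one item blank.
3. **MIDAS total at V6.** Extend the Appendix 1 multiple imputation to this score as a sensitivity analysis.

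**Cost.** SAP wording and modest programming, with no new data. Shift rates will be slightly lower. The model assumes data missing at random, and subjects who leave before V4 add no post-baseline data to it. Alignment with the diary rule is close but not exact: a subject leaving between Day 70 and V6 is scored from observed diary data there but counted as not shifted on MIDAS, which is one reason for the observed-case analysis alongside.

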### **8.2 Subject Disposition**

The number and percentage of subjects enrolled, randomized, treated at least one time, completing/withdrawing from each period and from the study overall will be tabulated for each treatment

group and overall. Reasons for early withdrawal will be summarized by treatment group using numbers and percentages of subjects.

The number of subjects included and excluded from the analysis populations (safety, ITT, and PPS) will be summarized for each treatment group. In addition, the reason(s) for exclusion from each population will be summarized.

### **8.3 Demographic and Baseline Characteristics**

Descriptive statistics of demographic variables (e.g. age, gender and race), and other baseline characteristics will be presented for the safety population by treatment group and overall. For quantitative variables, all summaries will include the number of non-missing observations, mean, median, standard deviation, minimum, and maximum. For qualitative variables, the summaries will include the number and percentage of subjects within each category for the outcome.

### **8.4 Efficacy Analyses**

#### **8.4.1 Primary Efficacy Analysis**

The primary efficacy analyses will be performed on the ITT population and will be repeated in the PP population, if the sample size between the two groups differ by more than 5%.

Summary statistics for the primary variable, change from 4-week run-in period, will be presented by treatment group. Missing data will be imputed per section 7.4.1.

The number of migraine days will be summarized descriptively for each study phase (run-in and DB) and by treatment group. The summary statistics for each visit, change between the double-blind and 4-week run-in period and percentage change between the double blind and 4-week run-in period (a secondary endpoint) will be summarized by mean, standard deviation, median, minimum, and maximum.

The two-sided, 95% confidence interval (CI) of the difference between the two device groups (active minus sham) in change from 4-week run-in period will be produced and the p-value will be calculated based on a two-sample t-test. If the p-value from the two-sample t-test is less than 0.05, then the null hypothesis will be rejected.

As sensitivity analyses, the two groups will be compared using analysis of covariance (ANCOVA) models with change from 4-week run-in period as the dependent variable and treatment group, and center as fixed effects with the number of migraine days in the 4-week run-in period as a covariate and again with treatment group, center, and aura as fixed effects with number of migraine days in the 4-week run-in period as a covariate. The adjusted means, adjusted mean difference and 95% confidence interval for the adjusted mean difference based on the ANCOVA models will be reported. The p-values tests that the adjusted mean difference between groups at Month 3 equals zero will be reported.

Further sensitivity analyses will investigate the robustness of the analysis to missing data (missing data refers to data points imputed in the calculations presented in section 7.4.1) by implementing multiple imputation and the pattern-mixture model (PMM) with control-based pattern imputation as summarized by Ratitch and O'Kelly (2011). This PMM sensitivity analysis addresses the possibility that the missing data is missing not at random (MNAR), meaning the missing data is not independent of the unobserved outcomes

even after conditioning on the observed data. Please see Appendix 1 for a more detailed description of the steps to implement the multiple imputation and PMM models.

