**Figure 1: Diagram of Study Design**

### 3.2 Randomization

Subjects will be randomized to either the active treatment arm or sham control arm (allocation 1:1) under a randomized variable block design, stratified by study site.

Subjects will be randomized using Merge eClinical OS Interactive Web Response system (IWRS) via computer key board data entry for a web based interface.

The site personnel (the investigator or his designee) will enter the required study and subject information and will then be provided with a subject randomization number and device serial number. Once subject numbers, serial numbers, and randomization numbers have been assigned, they cannot be reassigned.

The IWRS will provide the site personnel confirmation of the randomization number and device serial number assigned to each subject.

A sponsor designee will also have a copy of the randomization schemes for each study site and will be responsible for providing the un-blinded trainer with the randomization schemes.

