### 3.5 Sample Size

Table 1 provides the required sample size per treatment group when the number of migraine days per 28-day period is used as the primary outcome measure. Sample size calculations are based on the clinically meaningful difference between active and sham treatment groups in change from baseline. Assuming a type I error of 5% (two-sided) and 90% power, Table 1 displays the required sample sizes for different values of the common standard deviation (2.0, 2.5, 3.0 and 3.5) and the presumed difference between treatment groups (1, 1.5 and 2 days). Selecting an improvement of 1 day and a common standard deviation of 2.5 requires 133 subjects per treatment group. With 15% drop-out during the randomized treatment period, a total of 160 subjects per treatment group (or 320 subjects total) would need to be randomized.

**Table 1: Required Sample Size per Treatment Group  
Assuming Type I Error ( $\alpha$ ) = 5% (two-sided) and 90% Power**

Variability (Common SD*, $\sigma$ )	Clinically Significant Improvement: Active – Sham = $\Delta$		
	1-day	1.5-day	2-day
2.0	86	--	--
2.5	133	60	34
3.0	191	86	49
3.5	259	115	66

\*Estimated standard deviation for change from baseline. Standard deviations for baseline and post treatment scores are between 2.0 to 3.5.

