#### **8.4.3.6 Pooling Analyses**

Poolability of study sites will be assessed by comparing change in migraine days= trt\*site interaction; if  $p < 0.10$ , results will be stratified by site. Sites with less than five (5) subjects enrolled will be combined into a pseudo-site for purposes of analysis. To protect against having an overly large pseudo-site, when one

pseudo-site exceeds ten subjects, a second pseudo-site will be formed. This process will continue as needed each time a pseudo-site exceeds ten subjects.

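### The primary decision rests on an unadjusted t-test of change; the site- and run-in-adjusted ANCOVA already in the SAP is generally more precise and should carry it

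*SAP*

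**What the plan says.** - **Decision rule.** Section 8.4.1 compares the groups on change from the run-in period, and "the p-value will be calculated based on a two-sample t-test". The null hypothesis is rejected if that p-value is below 0.05. The confidence interval is for the unadjusted difference.
- **ANCOVA.** The same section continues: "As sensitivity analyses, the two groups will be compared using analysis of covariance (ANCOVA) models". The first model has treatment and center as fixed effects and run-in migraine days as covariate. The second adds aura.
- **Randomization.** Section 3.2 allocates subjects 1:1 "under a randomized variable block design, stratified by study site".
- **Sample size.** Section 3.5 is built on the t-test: "Assuming a type I error of 5% (two-sided) and 90% power", a 1-day difference and an SD of change of 2.5 give 133 per group. The footnote to Table 1 adds: "Standard deviations for baseline and post treatment scores are between 2.0 to 3.5". Allowing for attrition: "With 15% drop-out during the randomized treatment period, a total of 160 subjects per treatment group".
- **Missing outcome.** For a subject with fewer than 70 study days, section 7.4.1 states that "the month 3 value will not be calculated, but rather imputed to the run-in value", which makes the change zero.
- **Small sites.** Section 8.4.3.6: "Sites with less than five (5) subjects enrolled will be combined into a pseudo-site for purposes of analysis". It does not say which small sites join which pseudo-site.

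**The concern.** The test that decides the trial omits the factor used to stratify randomization. It also treats run-in migraine days in a fixed way: a change score sets the slope of the Month 3 count on the run-in count at exactly 1. When the true slope differs from 1, as regression to the mean usually makes it, the change score stays correlated with run-in. That part of the variance could be removed and is left in the error term.

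Two things are at stake. The confirmatory p-value and interval come from the less precise of two prespecified analyses. And in any one trial, a chance difference between arms in run-in migraine days moves the primary estimate. The ANCOVA would correct for this, but under section 8.4.1 it cannot carry the decision. The SAP gives no reason for this order. Elsewhere it treats center and run-in count as worth adjusting for: both are in the logistic sensitivity models of section 8.4.2 and in the imputation models of Appendix 1.

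**Working it through.** **1. Reproduce the SAP's sample size.** With a difference of 1 day, SD 2.5, two-sided 5% and 90% power, the noncentral-t calculation gives 133 per group (power 90.1%; 132 gives 89.9%), as stated. Dropout: 133/0.85 = 156.5, so 157; the SAP uses 160, which leaves 160 × 0.85 = 136 evaluable per arm. T-test power at 136 is 90.8%.

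**2. Correlation implied by the SAP's SDs.** The SAP states no correlation. With equal baseline and post SD s, Var(change) = 2s²(1 − ρ) = 2.5² = 6.25, so ρ = 1 − 6.25/(2s²).

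**3. Gain without imputation (136 per arm, 1-day effect).** The ANCOVA residual variance is s²(1 − ρ²), so its ratio to the variance of change is (1 + ρ)/2.

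| s | ρ | Variance ratio | ANCOVA power | t-test power |
|---|---|---|---|---|
| 2.0 | 0.219 | 0.61 | 98.8% | 90.8% |
| 2.5 | 0.500 | 0.75 | 96.7% | 90.8% |
| 3.0 | 0.653 | 0.83 | 95.1% | 90.8% |
| 3.5 | 0.745 | 0.87 | 94.0% | 90.8% |

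**4. Unequal SDs.** In general ρ = (s₀² + s₁² − 6.25)/(2s₀s₁) and the residual variance is s₁²(1 − ρ²), where s₀ is the baseline SD and s₁ the post SD. Over all pairs between 2.0 and 3.5, the ratio to 6.25 runs from 0.31 (s₀ = 3.5, s₁ = 2.0) to 1.00 (for example s₀ = 2.5, s₁ = 3.5) and never exceeds 1. It reaches 1.00 only where the slope is 1.

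**5. Gain under the zero-change rule of section 7.4.1.** Assumptions: 160 analysed per arm; a share p = 0.15 imputed, independently of run-in; a 1-day effect in the rest, so 0.85 day overall; equal SDs; sham mean change 0 or -3 days (active -1 or -4) among the rest.

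- Variance of change per arm: (1 − p) × 6.25 + p(1 − p)m², where m is the arm's mean change. Summed over arms: 5.3125 + 5.44 = 10.7525 (sham 0), or 6.46 + 7.3525 = 13.8125 (sham -3).
- Part explained by run-in, per arm: (1 − p)²(1 − ρ)²s² = 1.764, 1.129, 0.784 and 0.576 for s = 2.0, 2.5, 3.0 and 3.5.

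| s | Sham 0: variance cut | Sham 0: ANCOVA power (t-test 90.5%) | Sham -3: variance cut | Sham -3: ANCOVA power (t-test 82.2%) |
|---|---|---|---|---|
| 2.0 | 32.8% | 97.9% | 25.5% | 91.7% |
| 2.5 | 21.0% | 95.7% | 16.3% | 88.4% |
| 3.0 | 14.6% | 94.3% | 11.4% | 86.5% |
| 3.5 | 10.7% | 93.3% | 8.3% | 85.4% |

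The gain is about 3 to 9 percentage points. The 95% CI half-width falls from 0.51–0.58 day (t-test) to 0.42–0.55 day (ANCOVA).

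**6. Chance run-in imbalance.** One standard error is s√(2/160) = 0.22 to 0.39 day. It shifts the t-test estimate by 0.85(1 − ρ)s√(2/160) = 0.148 day (s = 2.0) to 0.085 day (s = 3.5).

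**7. Finite-sample check by simulation, with center in the model.** The SAP gives no number of centers, so these are assumptions.

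- 20 sites of 16, with the zero-change rule: power for t-test and ANCOVA was 90.5% and 98.0% (s = 2.0, sham 0), and 81.4% and 84.1% (s = 3.5, sham -3). With a site share of variance of 0 or 5%, type I error was 4.3–5.1% (t-test) and 4.4–5.5% (ANCOVA).
- 10, 27 or 53 centers without imputation, SDs 2.5 and ρ = 0.5, between-center SD 1 day: t-test type I error was 3.3–3.9% and power about 88%. ANCOVA gave 4.3–4.8% and 96–97%.
- Least favourable case (slope 1, no center effect, 53 centers of 5): the ANCOVA standard error was about 2% larger, with power 89.3% against 89.9%, within simulation error.

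**The case against.** The best defence is that nothing here is wrong. The t-test is unbiased over randomizations and matches both the hypothesis in section 3.3 and the sample size in section 3.5. On the SAP's own planning basis it has 91% power. Its interval already allows for chance imbalance in run-in. Both ANCOVAs will be reported with estimates, intervals and p-values, so any imbalance will be visible. All of this stands, and it is why the point concerns efficiency and not validity. It does not answer why the less precise analysis should decide: if the two disagree, the SAP binds the sponsor to the t-test.

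The size of the gain is fairly challenged. The tabulated gains need equal baseline and post SDs, which the SAP does not state. With SDs of 2.0 at baseline and 3.0 post, the ratio is 0.98 and the gain negligible. The fall of t-test power to 82% comes from the zero-change rule combined with an assumed sham change of -3 days, and ANCOVA does not repair that rule. Also, 160 analysed per arm is an upper bound, because the ITT definition in section 5.1 drops subjects without a verified treatment. Nor need every dropout be imputed: 70 to 83 study days still yields a computed value. These points widen the range of the gain but do not reverse its direction.

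That center terms cost degrees of freedom is true but minor: 0.1 point of power or less with 20 centers (assumed), and about 2% in standard error in the worst case simulated. The section 8.4.3.6 rule on site interaction applies whichever test is primary.

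**Conclusion.** The concern holds, as a change that should be made and not as a validity error. The direction is secure: over the SAP's whole SD range the large-sample ANCOVA variance is never above that of the t-test. Only with a slope near 1 and many very small centers could ANCOVA lose slightly.

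The size is less certain. With equal SDs, the variance falls by 13–39% on the planning basis, or by 8–33% under the imputation assumptions above. If the SDs differ, the gain lies anywhere from nil to larger (variance ratio 1.00 to 0.31 without imputation). Nothing in this point suggests an inflated type I error; if sites differ, the t-test errs slightly on the conservative side.

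**What to change.** Before unblinding:

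1. Make the first ANCOVA of section 8.4.1 (treatment and center as fixed effects, run-in migraine days as covariate) the primary test and the source of the primary 95% CI. Keep the two-sample t-test as a sensitivity analysis.
2. Use the pooling rule of section 8.4.3.6 for the center term, and complete it by stating which small sites go into which pseudo-site.
3. Use the same model, with the matching run-in value as covariate, for the changes in headache days and acute-medication days.

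The sample size need not change and no extra data are needed. The cost is low but not nil: SAP wording, the pseudo-site assignment, and alignment with the protocol, which was not available here, if it names the t-test. Section 4 already has the SAP finalized before database lock and unblinding. The zero-change imputation in section 7.4.1 needs separate consideration, since this change leaves it as it is.
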